7.1.6 Handling of Missing or Partial Dates

In cases of incomplete dates for AEs or non-study medications, the missing component(s) will be assumed as the most conservative value(s) possible. For example, the imputation rule is to conservatively capture AEs with missing start dates as treatment-emergent AEs (TEAEs). Actual data values, as they appear in the clinical database, will be shown in the data listings. Rules for partial dates are described in Table 7-2.

Table 7-2 Rules for Missing or Partial Dates

Parameter	Missing	Additional Conditions	Imputation
Start date for AEs	D only	M and Y same as M and Y of first dose of study drug	Date of first dose of study drug
		M and/or Y not same as M and Y of first dose of study drug	First day of non-missing month
	D and M	Y same as Y of first dose of study drug	Date of first dose of study drug
		Y not same as Y of first dose of study drug	Use Jan 1 of non-missing year
	M, D and Y	None – date completely missing	Date of first dose of study drug
Stop date for AEs	D only		Last day of non-missing month
	D and M		Use Dec 31 of non-missing year
	M, D and Y	Deceased	Date of death
		Not deceased	Date of the end of trial participation

Parameter	Missing	Additional Conditions	Imputation
Start date for non-study medications	D only	M and Y same as M and Y of first dose of study drug	Date of first dose of study drug
		M and/or Y not same as M and Y of first dose of study drug	First day of non-missing month
	D and M	Y same as Y of first dose of study drug	Date of first dose of study drug
		Y not same as Y of first dose of study drug	Use Jan 1 of non-missing year
	M, D and Y	None – date completely missing	Date prior to date of first dose of study drug
	Stop date for non-study medications	M and Y same as M and Y of first dose of study drug	Last day of non-missing month
		M and/or Y not same as M and Y of first dose of study drug	Last day of non-missing month
	D and M	Y same as Y of first dose of study drug	Use Dec 31 of non-missing year
		Y not same as Y of first dose of study drug	Use Dec 31 of non-missing year
	M, D and Y	None – date completely missing	Date will not be imputed

Notes: D=Day, M=Month, Y=Year

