12.3 Reporting Period

The reporting period for adverse events begins when the subject provides written informed consent and extends until 28 calendar days after the last dose of the investigational product is administered. All adverse events that occur during this period and are known to the investigator must be reported according to the requirements outlined in [Section 12.4](#).

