7.3.1 Adverse Events

Adverse events (AEs) are defined as any untoward medical occurrences in subjects administered the study treatment, whether or not they have a causal relationship to the treatment. All reported terms (investigator descriptions) for AEs will be coded using the most recent version of the MedDRA. TEAEs are defined as any AEs that occurred or worsened after the first randomized study medication; regardless of on-treatment or off-treatment periods. All TEAEs will be summarized with frequencies and percentages of subjects by treatment group, system organ class (SOC), and preferred term (PT). The frequencies and percentage of subjects with any AE across all SOCs will be summarized by treatment group. The AEs occurring prior to receiving the first randomized dose are defined as pre-treatment AEs and will be listed only.

TEAEs leading to discontinuation of study drug, TEAEs related to study drug, serious TEAEs, and TEAEs by maximum severity will be summarized and listed. Deaths will be listed if any. An overall summary of the above categories by treatment group will also be provided. All AEs leading to discontinuation from study, serious AEs, and death will be provided in listings.

TEAEs of special interest including AEs that require initiation or modification of antihypertensive therapy will be summarized separately, if applicable.

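### SAP Table 7-2 sets an adverse event's missing start date to the first dose without checking its stop date, so an event that ended before dosing can be counted as treatment-emergent

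*SAP*

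**What the plan says.** SAP 7.1.6 states a general principle for incomplete dates, that "the missing component(s) will be assumed as the most conservative value(s) possible", and gives as its example that "the imputation rule is to conservatively capture AEs with missing start dates as treatment-emergent AEs".

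Table 7-2 has five rows for adverse event start dates. Three of them assign the date of first dose. Their conditions are:

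- day missing: "M and Y same as M and Y of first dose of study drug";
- day and month missing: "Y same as Y of first dose of study drug";
- everything missing: "None – date completely missing".

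The other two rows, for a month or year different from that of first dose, assign the first day of the known month or 1 January of the known year. A stop date with only the day missing becomes the last day of its month. No row, note or surrounding sentence compares an imputed start with the stop date.

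On collection, Protocol 12.3 says that "The reporting period for adverse events begins when the subject provides written informed consent". Protocol 10.2 has events recorded at both baseline days, and drug is dispensed only after the baseline ABPM recording has been verified.

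On classification, SAP 7.3.1 counts as TEAEs the events that occurred or worsened after the first randomized medication, and adds: "The AEs occurring prior to receiving the first randomized dose are defined as pre-treatment AEs and will be listed only".

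**The concern.** Calling an event treatment-emergent when its timing is unknown is a sound, cautious convention. It stops being sensible once the record itself shows that the event was over before the first capsule was taken. Such events can be in the database, because collection starts at consent and Protocol 10.1 allows about four weeks between screening and randomization.

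For these events two sections of the SAP disagree: Table 7-2 makes them TEAEs, and 7.3.1 keeps them out of the TEAE tables. Two programmers could resolve this differently. Under the Table 7-2 reading, the analysis data contain impossible start and stop pairs, and the TEAE summaries contain events that drug cannot have caused. Because 7.1.6 keeps the raw dates in the listings, a reader could also find a tabulated TEAE whose listed stop date is before first dose.

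**Working it through.** The plan gives no figure to reproduce, so the check is to apply the Table 7-2 rows as written to test records. The dates are invented for illustration: first dose 20 March 2022. Duration is stop − start + 1, in days.

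| Recorded start | Recorded stop | Start under Table 7-2 | Stop used | Duration | Start after stop? |
|---|---|---|---|---|---|
| March 2022, day missing | 10 Mar 2022 | 20 Mar 2022 | 10 Mar 2022 | 10 − 20 + 1 = −9 | Yes |
| 2022, day and month missing | 10 Mar 2022 | 20 Mar 2022 | 10 Mar 2022 | −9 | Yes |
| Wholly missing | 10 Mar 2022 | 20 Mar 2022 | 10 Mar 2022 | −9 | Yes |
| 2022, day and month missing | February 2022, day missing | 20 Mar 2022 | 28 Feb 2022 | −20 + 1 = −19 | Yes |
| February 2022, day missing | 10 Mar 2022 | 1 Feb 2022 | 10 Mar 2022 | 38 | No |
| 2021, day and month missing | 10 Mar 2022 | 1 Jan 2021 | 10 Mar 2022 | 434 | No |
| March 2022, day missing | March 2022, day missing | 20 Mar 2022 | 31 Mar 2022 | 31 − 20 + 1 = 12 | No |

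The first four records ended before first dose, yet each gets the first-dose date as its start and so becomes a TEAE. The next two show that the rows for a different month or year cause no conflict. The last shows a limit on the day-missing row: if the stop also lacks its day in the same month, the month-end rule puts the stop after first dose. That event is not known to be pre-dose, and counting it is what the rule intends.

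Now apply the condition that the first-dose date is used only when the stop (after any partial-date imputation) is missing or on or after first dose. The first four records become pre-treatment under 7.3.1. The last three are unchanged, and an event with no stop date is still captured as a TEAE.

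**The case against.** The strongest reply is that the text already resolves the conflict. 7.1.6 asks for the most conservative *possible* value, and a start after the recorded stop is not possible. Table 7-2 only imputes dates, while 7.3.1 classifies events, and an event that ended before dosing neither occurred nor worsened afterwards. This is a fair reading of the intent, and a careful programmer might adopt it. It does not remove the problem: the table is explicit, has no such exception, and yields the wrong result if followed.

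Other limits stand in full:

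- **Consequences.** SAP 7.3.1 plans no analysis of event duration and no between-group test of TEAEs, and the listings show raw dates. A reader might infer a bias between arms or a material dilution of differences. Nothing in the documents supports that, since pre-dose events should not depend on the arm.
- **Serious events.** Protocol 12.4.1 requires notice within one business day and detailed follow-up. A serious pre-dose event with a known stop but an unresolved start should be rare.
- **Frequency.** A reader might infer that about half of pre-dose events with a missing day, and nearly all with day and month missing, are misclassified. If starts are uniform over a 28- to 31-day pre-dose period, about 48–52% and 96% of such starts do fall in the first-dose month and year respectively. But those shares cover all pre-dose starts with that kind of missingness, including events that continue past dosing or have no known stop, which the rule deliberately captures. They also assume the longest screening period: with 14 days the day-missing share would be about 75%, and with 7 days about 87%. They do not measure this defect.
- **Visit of first recording.** It is tempting to say that any event first recorded at Visit 2A, or at 2B before dispensing, is pre-treatment. 7.3.1 does not support that, because an event present before dosing that worsens afterwards is a TEAE.

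**Conclusion.** Wrong as written, minor. In three of the five start-date rows, Table 7-2 gives an event that stopped before first dose a start later than its stop and makes it a TEAE, against SAP 7.3.1. The convention for events of unknown timing is not at fault; only the exception for a known pre-dose stop is missing.

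The effect is small. It needs an incomplete start date together with a recorded or imputed stop before first dose, and the number of such events cannot be derived from the documents. Similarity across arms rests on the assumption that randomization balances pre-dose events and the quality of their dates. The likely result is a slight rise in TEAE counts in every group. The primary and secondary blood pressure analyses do not use these dates.

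**What to change.** Add one note to the adverse event start-date rows of Table 7-2, to this effect: the date of first dose is imputed only when the stop date, after any partial-date imputation, is missing or on or after first dose; an imputed start may not be later than the stop date; an event whose stop date is before first dose is pre-treatment and handled under 7.3.1.

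The condition should rest on the stop date alone. A clause based on the visit of first recording should not be added, because it would remove events that worsen after dosing from the TEAE tables.

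The cost is one line in the SAP and one condition in the program that derives the adverse event dates. No new data are needed, and events of truly unknown timing are still counted as treatment-emergent.

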7.1.7 Handling of Missing Efficacy Data

Every effort will be made to obtain the protocol-required data for all subjects according to the study schedule. However, subjects may withdraw from the study prior to completion, or discontinue study medication for any reasons. For subjects who discontinue treatment prior to study completion, every attempt will be made to obtain end of study ABPM assessments prior to their discontinuation of treatment or initiation of changes to concomitant antihypertensive medications or prohibited treatments for diabetes or weight loss. Missing data imputation methods and sensitivity analyses are discussed in each of the endpoint analysis section.

To retain as much observed data as possible, the imputation of missing data will proceed after unscheduled visits have been mapped to analysis visits, if applicable. Refer to [Section 7.1.5](#) for handling multiple observations and unscheduled visits.

7.2 Efficacy Analyses

7.2.1 Primary Efficacy Analysis

The primary efficacy endpoint of change in mean SBP obtained from 24-hr ABPM from baseline to Week 8 (or imputed Week 8 values for early termination subjects) will be evaluated on the PP population. An analysis of covariance (ANCOVA) model will be used to evaluate between-group differences in changes from baseline (top-dose VI-0521 vs. placebo and top-dose VI-0521 vs. phentermine) in 24-hr mean SBP. Factors included in the model are

treatment (VI 0521, phentermine, and placebo), sex (male and female), age (< 50 ; ≥ 50 years), and hypertensive status (no medical diagnosis of or treatment for hypertension; medical diagnosis of hypertension treated with 0-2 antihypertensive agents; or medical diagnosis of hypertension treated with 3 or more antihypertensive agents). Baseline values of 24-hr mean SBP will be adjusted in the model as a covariate. Adjusted means (LS Mean \pm standard error) with associated two-sided 95% confidence intervals for the between-treatment comparisons and for the changes from baseline will be reported.

If the upper bound of the two-sided 95% confidence interval for the between-treatment group difference (VI-0521 minus placebo or phentermine) in change from baseline in 24-hr mean SBP is less than 3 mmHg, success for a non-inferiority test will be claimed and the null hypothesis will be rejected. If the upper bound of the two-sided 95% confidence interval is less than 0 mmHg, i.e., with a p-value less than 0.05 significance level, superiority will be claimed.

The estimand, estimator, and estimate of this primary endpoint are defined as follows:

Estimand	Population	Per Protocol
	Endpoint	Changes from Baseline in mean SBP obtained from 24-hr ABPM at Week 8
	How to account for intercurrent events	The treatment policy strategy will be followed, whereby the observed value (if not missing) for the endpoint of interest will be used for analysis.
	Population-level summary	The between-treatment difference in changes from baseline to Week 8 in mean SBP from 24-hr ABPM.
Estimator	Analysis	ANCOVA with treatment, stratification factors (sex, age and hypertensive status) and baseline value of 24-hr mean SBP as a covariate.
Estimates	Primary to support the estimand	Between-group comparison (effect in VI-0521 minus effect in placebo [or phentermine]): ✓ LSM for the between-group difference ✓ 95% CI of the LSM ✓ p-value
	Tributary	Within-treatment group comparison (effect at Week 8 minus the value at baseline): ✓ LSM for the within-group difference ✓ 95% CI of the LSM ✓ p-value

The following SAS programming codes will be applied:

```
PROC MIXED DATA=DATAIN;
  CLASS TREATMENT(REF='Placebo' [or 'Phentermine']) SEX AGE HYPSTATUS;
  MODEL CHG_SBP=TREATMENT SEX AGE HYPSTATUS BASE_SBP/SOLUTION DDFM=KR;
  LSMEANS TREATMENT/ALPHA=0.05 PDIFF CL;
```

RUN;

For subjects who discontinue from the study but complete Early Termination ABPM assessments, such measurements will be mapped to Week 8/End of Study or Early Termination for analysis. For subjects who have missing 24-hr SBP measurements at baseline or at Week 8 after mapping unscheduled visits, missing data will be imputed using the approach below. If the percentage of missing readings at either visit is $\leq 25\%$ (see [Section 5.4](#)), 24-hr mean SBP values will be calculated by taking the average of non-missing and imputed measurements over the 24-hr time period. Imputed measurements will be derived as follows:

1. For any intermediate missing observations between two non-missing readings BP_1 and BP_2 , missing observations will be imputed using the formula: $BP = (BP_2 - BP_1)/(t_2 - t_1) \times (t - t_1) + BP_1$; whereas t_1 , t , and t_2 are the time of the measurements respectively;
2. If missing observations are at the beginning or at the end, the beginning observations will be imputed as the average of non-missing and step 1 imputed data points from 6:00 to 22:00 hours. The end observations will be imputed similarly using data points from 22:01 to 5:59 hours.

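### SAP 7.2.1's LSMEANS line gives each hypertensive-status level one third of the weight in every within-arm mean change; between-arm tests are unaffected, but observed margins would suit these estimates better

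*SAP*

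**What the plan says.** SAP 7.2.1 presents its PROC MIXED program as the code to be used, whereas later code in the SAP is labelled as an example. The model line is "MODEL CHG_SBP=TREATMENT SEX AGE HYPSTATUS BASE_SBP/SOLUTION DDFM=KR". Sex, age and hypertensive status are CLASS factors, and there is no treatment-by-stratum interaction. The adjusted means come from "LSMEANS TREATMENT/ALPHA=0.05 PDIFF CL".

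The SAP commits to adjusted means with standard errors and 95% intervals "for the between-treatment comparisons and for the changes from baseline will be reported". In the estimand table, the Tributary row lists a "Within-treatment group comparison (effect at Week 8 minus the value at baseline") with an LS mean, a 95% CI and a p-value. SAP 7.2.2 repeats that row for the secondary endpoints, and SAP 7.2.3 uses similar models for the exploratory changes.

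The population-level summary of the estimand is between-arm only: "The between-treatment difference in changes from baseline to Week 8 in mean SBP from 24-hr ABPM". The third level of hypertensive status is "medical diagnosis of hypertension treated with 3 or more antihypertensive agents". Neither document gives its expected share, a quota or a cap, and neither says which mix of strata the within-arm means should describe.

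**The concern.** By default, LSMEANS averages over the levels of each CLASS factor with equal weights and holds the covariate at its overall mean. Each arm's adjusted change is therefore the mean for a population that is one third untreated or undiagnosed, one third on 0 to 2 agents and one third on 3 or more, half male, and half under 50.

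The third stratum could well be small. Protocol 8.1 asks for only one weight-related comorbidity, which need not be hypertension, and nothing in the plan pushes that stratum towards one third. If it is small, a few subjects carry a third of each arm's mean. The interval is then wider than the data require, and the estimate describes a mix the trial did not analyse. Readers will look at these figures to see whether ambulatory SBP rose or fell on each treatment.

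**Working it through.** **Inputs from the documents.** SD of change 10 mmHg, difference or margin 3 mmHg, 80% power, two-sided 0.05 (one-sided 0.025 for non-inferiority), 5% dropout, 185 per arm (SAP 8).

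**The plan's own figure.** 2 × (1.960 + 0.842)² × 10² / 3² = 174.4, so 175 per arm; 175 / 0.95 = 184.2, so 185. The stated size is reproduced. After 5% dropout, 185 × 0.95 = 175.75, taken as 176 per arm (528 in total).

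**Assumptions (not in the documents).** Residual SD 9 mmHg after adjustment; 70% female; 55% aged 50 or over; share p₃ on 3 or more agents of 2, 5, 10 or 20%, with the other two strata equal at q = (1 − p₃)/2; factors independent of each other and balanced across arms. The baseline term is left out because it sits at the overall mean under both weightings.

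**Formula.** With n per arm and N = 3n:

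- Observed margins: SE = σ × √(1/n)
- Equal weights: SE = σ × √(1/n + (H + S + A)/N)
- H = 2(1/3 − q)²/q + (1/3 − p₃)²/p₃
- S = (0.5 − 0.7)²/(0.7 × 0.3) = 0.190
- A = (0.5 − 0.55)²/(0.55 × 0.45) = 0.010

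Observed margins give 9 × √(1/176) = 0.68 mmHg at any share. For p₃ = 5%, H = 2(0.1417²)/0.475 + 0.2833²/0.05 = 1.690, so the equal-weight SE is 9 × √(0.005682 + 1.891/528) = 0.87 mmHg.

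| Share p₃ | Subjects in stratum (of 528) | H | SE, equal weights | SE, observed margins | Ratio |
|---|---|---|---|---|---|
| 2% | 10.6 | 5.009 | 1.12 | 0.68 | 1.65 |
| 5% | 26.4 | 1.690 | 0.87 | 0.68 | 1.28 |
| 10% | 52.8 | 0.605 | 0.76 | 0.68 | 1.13 |
| 20% | 105.6 | 0.111 | 0.71 | 0.68 | 1.05 |

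Inverting the design matrix gives the same values. The ratio depends on neither σ nor n at fixed shares, so a smaller per-protocol set does not change it. With sex and age both 50:50 the ratios are 1.63, 1.25, 1.10 and 1.02, and at a one-third share the two weightings coincide.

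**Power.** For an illustrative true within-arm change of 2 mmHg at a 5% share, Φ(2/SE − 1.96) gives Φ(0.35) = 64% with equal weights and Φ(0.99) = 84% with observed margins.

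**Shift in the estimate.** If the third stratum's baseline-adjusted change differs from the other two by g, every arm's mean moves by (1/3 − p₃) × g. For g = 3 mmHg (illustrative) this is 0.94, 0.85, 0.70 and 0.40 mmHg at 2, 5, 10 and 20%. For g = 0 it is zero. Sex and age levels add shifts in the same way: |0.5 − 0.7| = 0.20 and |0.5 − 0.55| = 0.05 times their own differences under these shares.

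**Validity of the within-arm test.** In a simulation of the full model with baseline SBP (176 per arm, residual SD 10, 5% share, 75% female, 60% aged 50 or over), a true change of zero in every stratum was rejected in 5.2% of data sets with equal weights and 5.3% with observed margins.

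**Between-arm difference.** The stratum terms cancel in an additive model. The SE is 9 × √(2/176) = 0.96 mmHg under both weightings, and the simulated differences and SEs were identical in every data set.

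**The case against.** The case for leaving the code alone has several parts.

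- Equal-weight LS means are the software's conventional form. The SAP promises LS means without stating weights, so text and code agree. This stands: there is no contradiction to correct, only an unstated target.
- The stratum need not be small. The 140/90 screening limit applies to subjects on stable treatment, and a fixed-dose combination counts as two agents, so one combination plus one further drug reaches the third level. This also stands. The share is unknown, and near 20% the gain is slight.
- Other outputs help. SAP 7.1.1 provides raw descriptive summaries and SAP 7.2.1.3 plans analyses by hypertensive status, so readers do not depend on the adjusted mean alone. This limits the harm but does not make the adjusted mean describe the analysed subjects.
- The within-arm change is an uncontrolled quantity over 8 weeks, with lifestyle counselling in all arms, and is a secondary line in the estimand table. This stands and sets the severity.

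A reader might go further and infer that the within-arm p-value is wrong. The simulation does not support that: the test keeps its 5% level and differs only in power and in the population it refers to. A reader might also compare the possible shift with the 3 mmHg margin. That margin applies to between-arm differences, where the shift is exactly zero.

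**Conclusion.** The point holds as a minor reporting improvement. As coded, within-arm adjusted means describe an equally weighted population that nothing in the SAP says was intended. The loss of precision follows from the weighting alone: SEs are about 1.65, 1.28, 1.13 and 1.05 times the observed-margin SE at assumed shares of 2, 5, 10 and 20%, on the design mix assumed above. Correlation between age and hypertensive status, or unequal sizes of the other two strata, would change these ratios somewhat. A shift in the estimate is conditional on adjusted change differing between levels of hypertensive status, sex or age, and the documents give no figure for such differences.

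The documents do not support treating this as a threat to the trial's conclusions. The hypotheses in SAP 7.1.2, the hierarchy in SAP 7.1.2.1 and the tipping-point criteria all concern between-arm differences, which do not change.

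**What to change.** Add one sentence to SAP 7.2.1 stating that within-arm LS means target the analysed population, with margins pooled over arms, and change the line to `LSMEANS TREATMENT / ALPHA=0.05 PDIFF CL OM;`. Apply the same rule to the other ANCOVAs that report within-arm LS means: multiple imputation, secondary and exploratory. The public text does not show the ANCOVA code for those analyses, so check first whether they already set margins.

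The cost is one keyword and one sentence. The drawback is a departure from the software default, which a table footnote should state. No confirmatory estimate, interval or decision changes.
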